9.4 Serious Adverse Events

A serious adverse event (SAE) is defined as any untoward medical occurrence that meets any of the following criteria:

- a. Results in death
- b. Is life-threatening (defined as an event in which the participant was at risk of death at the time of the event and NOT an event that hypothetically might have caused death if it had been more severe)
- c. Requires inpatient hospitalization
- d. Prolongs an existing hospitalization
- e. Results in persistent or significant disability or incapacity
- f. Results in a congenital anomaly or birth defect
- g. Important medical event that requires an intervention to prevent any of a-f above.

- h. SAE qualifying as a SUSAR (serious unexpected suspect adverse reaction) will be subject to expedited reporting as per safety plan.

9.5 Adverse Event Collection Period

Collection of adverse events will commence from the time that the participant is first administered the study infusion (study hour =0). Routine collection of adverse events will continue until day 10. Any adverse events spontaneously reported to the investigator or observed by the investigator after day 10 will also be collected and recorded on the CRF.

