Secondary Safety Variables:	
Incidence of reported adverse events to include D28 and D60 in-hospital or telephone follow up

Safety Evaluations:	
In addition to vasopressor dependency index, the following laboratory values will be used for safety assessment at baseline and daily through study day 4 when available.
 
 1. Complete blood count with platelets 2. Basic Metabolic profile, including renal function 3. Liver function tests, including SGOT, SGPT, total bilirubin, and alkaline phosphatase 
Adverse events will be recorded prospectively, including incidences of hypotension, hepatitis (i.e., the elevation of liver enzymes), and injection site reactions.

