6.0 STUDY POPULATION AND ENROLLMENT

6.1 Participant Enrollment

Up to 66 participants will be enrolled. The study is expected to accrue over about 6-9 months. Participants will be recruited from the University of Arkansas for Medical Sciences Hospital. Additional

sites may be added at the discretion of the investigators and the sponsor. Participants who withdraw or prematurely discontinue study material infusion will be included in an intention to treat analysis. Safety data will continue to be collected up to hospital discharge for any participants who are withdrawn from the study.

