7.2.3 Clinical Outcome Assessments

ICU length of stay will be calculated in days from time = 0 to the earlier of ICU discharge or death. Any re-admissions to the ICU during the hospital stay will add days to ICU length of stay. Hospital length of stay will be calculated in days from time = 0 until the earlier of hospital discharge or death. A follow up at D28 and D60 will further evaluate the stated clinical outcomes.

Concomitant medications and adverse events will continue to be monitored and recorded in the CRF for the duration of the participant's hospital stay.

See the Schedule of Procedures in Appendix A for further details.

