9.0 ADVERSE EVENTS

Investigators will determine daily if any clinical adverse experiences occur during the period from enrollment to 48 hours after study drug termination. Most data normally collected as part of a clinical study to guarantee patient safety and determine efficacy is obtained as part of normal clinical care of patients in the hospital or ICU. Examples include arterial blood gases, electrolytes, liver function tests, hemograms, and chest radiographs. All available clinical data, including radiographs, laboratory values, vital signs, exam findings, and clinical impressions from the primary team, will be monitored for adverse events. The investigator will evaluate any changes in laboratory values and physical signs and will

determine if the change is clinically important and different from what is expected during treatment of patients with acute hypoxemic respiratory failure. If clinically important and unexpected adverse experiences occur, they will be recorded on the adverse event case report form. Investigators will report all serious and unexpected adverse events to the safety officer and the local IRB in a timely manner. All adverse events that are deemed non-serious and or not unexpected will be reported to the IRB annually at continuing review.

Patients will be closely monitored in a hospital or ICU setting. This will allow for prompt treatment of any adverse event that is suspected to be related to study drug, in which case the safety monitor will be notified and will evaluate the situation. In such an instance study drug infusion will be withheld until the event is evaluated and a decision has been made whether the infusion will be restarted or permanently discontinued.

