APPENDIX A: Schedule of Events

Measurement	Day 0 (baseline)	Day 1	Day 2	Day 3	Day 4	Day 5	Day 6	Day 7	Day 8	Day 9	Day 10	Day 11	Day 12-DC	Day 28 ^e Follow-up	Day 60 ^e Follow-up
Informed Consent	X														
Demographics- Hx & Px	X														
Eligibility Assessment	X														
Pregnancy Test	Xc														
Study Drug Administration		X	X	X	X	X	X	X	X	X					
Vital Signs		X	X	X	X	X	X	X	X	X	X	X	X		
Mean Arterial Pressure		Xa,b,d	X	X	X	X	X	X	X	X	X	X			
Vasopressor Dosages		Xa,b,d	X	X	X	X	X	X	X	X	X	X			
Basic Metabolic Panel		A	A	A	A	A	A	A	A	A	A	A			
CBC		A	A	A	A	A	A	A	A	A	A	A			
LFTs		Ab	A	A	A	A	A	A	A	A	A	A			
D-dimer blood draw		Xa,b	X		X		X		X		X		X		
CRP		Xa,b	X		X		X		X		X		X		
5 ml blood for citrulline etc.		Xa,b	X		X		X		X		X				
SaO2/ FiO2 ratio		X	X	X	X	X	X	X	X	X	X	X			
PaO2		X	X	X	X	X	X	X	X	X	X	X			
ABG		A	A	A	A	A	A	A	A	A	A	A			
Hospital status		X	X	X	X	X	X	X	X	X	X	X	X	X	X
ICU status		X	X	X	X	X	X	X	X	X	X	X	X	X	X
Non-invasive ventilation status		X	X	X	X	X	X	X	X	X	X	X			
Invasive ventilation status		X	X	X	X	X	X	X	X	X	X	X			
ConMed Review		X	X	X	X	X	X	X	X	X	X	X	X	X	X

Adverse Event Review		X	X	X	X	X	X	X	X	X	X	X	X	X	X	X
----------------------	--	---	---	---	---	---	---	---	---	---	---	---	---	---	---	---

a= measurement should be recorded or performed at hours 0, 2 and 12

b= Day 1 hour 0 samples/procedure must be collected/recorded before study drug is administered.

c= only perform if patient is of childbearing potential

d= must be collected 15 minutes prior to administration of study medication

e= Day 28 and Day 60 are telephone follow ups

X= Study Procedure A= Standard of Care

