## **STUDY DESIGN**

This is a randomized, double-blind, placebo-controlled, phase II study to evaluate the safety and efficacy of intravenous L-Citrulline in reducing the length of time from the start of study infusion to an intubation event in hospitalized acutely ill patients with an acute hypoxic respiratory illness due to COVID-19 infection (SARS-CoV2). Patients age of 18 years old and less than 65 years old inclusive with COVID-19 infection (SARS-CoV2) will be included in the study.

Only subjects hospitalized at UAMS and requiring oxygen for an acute hypoxic respiratory illness due to COVID-19 (SARS-CoV2) will be included in this study. Study drug administration will occur exclusively in the hospital.

In addition, subjects will receive standard supportive care for acute hypoxic respiratory illness and failure.

Approximately 60 participants ages 18 years to 65 years, inclusive, who meet all the inclusion criteria and none of the exclusion criteria will be randomized into the study over approximately 6-9 months.

The study consists of an initial Study Drug bolus followed by a continuous infusion for a maximum of 10 days. The safety and efficacy will be evaluated through hemodynamic monitoring, laboratory assessment, oxygenation status, and biomarker measurements through study day 10. Adverse events will be monitored through study day 10. Clinical outcomes, including all-cause mortality, ICU length of stay, and hospital length of stay will be assessed through hospital discharge.

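### The adverse event collection period is stated in four incompatible ways and the SAP names none for its adverse event table, so the reported incidence depends on which rule is applied

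*Protocol*

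**What the plan says.** The end of collection is given in four ways, all in current text:

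- **Drug stop plus 48 hours.** Protocol 9.0 has investigators look daily for adverse experiences "during the period from enrollment to 48 hours after study drug termination".
- **Day 10.** Protocol 9.5: "Routine collection of adverse events will continue until day 10". After that, only events volunteered to the investigator or noticed by the investigator are added. Protocol 5.1 also gives day 10, as does SAP Study Design: "Adverse events will be monitored through study day 10".
- **Hospital stay.** Protocol 7.2.3: "adverse events will continue to be monitored and recorded in the CRF for the duration of the" hospital stay. For withdrawn participants, 6.1 adds: "Safety data will continue to be collected up to hospital discharge for any participants who are withdrawn from the study".
- **D28 and D60.** The synopsis defines the secondary safety variable as "Incidence of reported adverse events to include D28 and D60 in-hospital or telephone follow up". In Appendix A the Adverse Event Review row is marked through the Day 60 column, with the footnote "Day 28 and Day 60 are telephone follow ups".

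The start differs too. Protocol 9.0 begins at enrollment, while 9.5 says "Collection of adverse events will commence from the time that the participant is first administered the study infusion".

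The documents also disagree about a patient weaned off oxygen before day 10. The synopsis, Protocol 5.1.2 and SAP Study Assessments say the patient leaves the study early. Protocol 11.5 says the drug is stopped but data collection goes on.

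The SAP lists incidence of adverse events in Table 2, without the D28/D60 extension, and number of adverse events under Secondary Safety Endpoints. Its adverse event method is a tabulation by severity and arm, with no risk period, time at risk or exposure adjustment.

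**The concern.** Comparing adverse event incidence with placebo is a stated objective in both documents. An incidence has meaning only with a defined period at risk, and here that period could end 2 days after an early drug stop or at day 60. Two sites, or a site and the programmer, could each follow the protocol and produce different tables.

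Two of the rules, drug stop plus 48 hours and hospital stay, also have a length that depends on the patient's course. The drug can stop because the patient has recovered enough to come off oxygen, or because of an adverse event (6.7). If treatment changes how soon either happens, one arm is watched for less time than the other. Under the trial's own hypothesis of respiratory benefit, the shorter window would tend to fall in the citrulline arm and make it look safer.

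The fixed day-10 rule has a gap of its own. A patient infused through day 10 has no routine collection after the infusion under 9.5, although 9.0 provides 48 hours.

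**Working it through.** The documents state no adverse event rate, expected count or time at risk, so there is no planned figure to reproduce. The conflict itself is shown by the passages above. The arithmetic below only sizes its consequences.

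**Inputs from the documents.** Maximum infusion 10 days (7.2.2); 48 hours after drug stop (9.0); day 10 (9.5); D28 and D60 (synopsis, Appendix A).

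**Assumptions, not in the documents.** A constant hazard of a first adverse event, λ = 0.03, 0.05 or 0.10 per day, identical in both arms; an exponential time to drug stop with mean m days, cut off at day 10; no death or loss to follow-up.

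**Formulas.**
- Fixed window of T days: incidence = 1 − exp(−λT).
- Drug stop plus 2 days: mean window = m(1 − exp(−10/m)) + 2. With a = 1/m, incidence = 1 − exp(−2λ) × [a/(a+λ) × (1 − exp(−10(a+λ))) + exp(−10(a+λ))].

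**Step 1: how far the rule moves the reported figure in one arm.**

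| Rule | λ = 0.03 | λ = 0.05 | λ = 0.10 |
|---|---|---|---|
| Drug stop + 48 h (m = 8) | 20.2% | 30.9% | 50.7% |
| Day 10 | 25.9% | 39.3% | 63.2% |
| D28 | 56.8% | 75.3% | 93.9% |
| D60 | 83.5% | 95.0% | 99.8% |

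Worked at λ = 0.05. Day 10: 1 − exp(−0.5) = 39.3%. Drug stop with m = 8: a + λ = 0.175; the bracket is 0.7143 × 0.8262 + 0.1738 = 0.7639; 1 − 0.9048 × 0.7639 = 30.9%. The D28 and D60 rows are too high if the hazard falls after recovery. They show the direction and the possible scale.

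**Step 2: gap between arms under the drug-stop rule, with no true difference in hazard.**

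| Mean stop time, placebo vs citrulline | Mean window (days) | λ = 0.03 | λ = 0.05 | λ = 0.10 |
|---|---|---|---|---|
| 8 vs 8 | 7.71 vs 7.71 | 0 | 0 | 0 |
| 8 vs 6 | 7.71 vs 6.87 | 2.0 points | 2.9 | 4.0 |
| 8 vs 5 | 7.71 vs 6.32 | 3.3 | 4.7 | 6.6 |
| 8 vs 4 | 7.71 vs 5.67 | 4.9 | 7.0 | 9.9 |

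For 8 vs 5 days the incidences behind the gaps are 20.2% vs 16.9%, 30.9% vs 26.1% and 50.7% vs 44.1%. Gaps were taken before rounding. The stop times are means before the day-10 cut-off.

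**Step 3: the same under a fixed window.** Both arms have the same T, so the expected gap is 0 at every λ, provided patients weaned off oxygen remain under collection. If they leave the study, as the synopsis and 5.1.2 say, the day-10 window is also shortened by recovery.

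**The case against.** The strongest reply is that the protocol has a section devoted to the collection period, 9.5, and it gives a fixed day 10. Protocol 5.1 and the SAP design section agree, and no document ties the endpoint analysis to drug stop plus 48 hours. Protocol 9.0 can be read as describing the investigators' daily surveillance. Protocol 11.5 keeps data collection going after an early stop, 9.5 still records later events that come to light, and Appendix A schedules adverse event review on Day 11, from Day 12 to discharge, and at D28 and D60. The SAP plans a descriptive table with no named test.

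Much of this stands. It rules out a stronger inference that a reader might draw: that the drug-stop rule gives the arms different observation times, so that their incidences are not comparable. The documents do not support that. The arms differ only if a drug-stop or discharge window is the one analysed and treatment changes time to stop or discharge. Equal stop times give a gap of zero, and the day-10 and D28/D60 windows are nominally the same in both arms. Nor is it right that nothing is scheduled after a full infusion; that follows only from reading 9.5 without Appendix A.

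The reply does not remove the inconsistency. The synopsis writes D28 and D60 into the endpoint definition itself, against day 10 in 9.5. Collection after day 10 is incidental in 9.5 and scheduled in Appendix A. Protocol 11.5 is contradicted by the early-exit text. The SAP's adverse event section does not say which events count.

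**Conclusion.** The point holds as an inconsistency that leaves a stated safety endpoint undefined. Collection has four incompatible ends and two starts, the status of patients weaned off oxygen is contradictory, and the SAP does not settle any of this for its table. The effect on the reported level can be large: at an assumed 0.05 per day, from about 31% to 95% depending on the rule.

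The risk to the arm comparison is conditional. It is 0 points if stop times are equal, and about 2 to 10 points in favour of the arm that stops sooner if mean stop times are 8 vs 6 to 8 vs 4 days and the 48-hour window is used. Those sizes rest on assumed hazards and stop times and on a constant hazard. They illustrate the problem and do not predict the trial's result. This is a secondary endpoint, so the change is advisable rather than critical, but the trial has no formal data safety monitoring board (11.4) and its adverse event table should be unambiguous.

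**What to change.** Reconcile Protocol 5.1, 7.2.3, 9.0, 9.5, the synopsis and Appendix A into one statement, and repeat it in the SAP:

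1. One fixed window for all adverse events, from hour 0, with the same end for every patient whatever the time of drug stop or oxygen weaning. Day 12 is one workable choice, since day 10 plus 48 hours covers the period in 9.0 after a full infusion.
2. A sentence saying that patients weaned off oxygen remain under adverse event collection, which removes the conflict between 5.1.2 and 11.5.
3. Adverse event review at D28 and D60 kept for all events, not only serious ones, as the synopsis and Appendix A now have it. Events with onset after the fixed window are reported separately.
4. Onset dates collected at the D28 call for patients discharged before the window ends, so that their events can be placed inside or outside it.
5. The same window named in the SAP adverse event section.

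The cost is small. Appendix A already schedules the contacts, so the work is mainly wording. The drawback is that some onset dates for patients discharged early will rest on recall at D28.

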10.0 STATISTICAL METHODS

10.1 Analysis Populations

The intent-to-treat (ITT) population will be used for all efficacy and safety analyses. This will consist of all randomized patients irrespective of whether the patient received study drug or the patient's compliance with the study protocol, in the treatment group assigned by the randomization system.

10.2 General Statistical Approach

Before database lock, a statistical analysis plan (SAP) will be issued as a separate document, providing full detailed methods for the analyses outlined below. Multiplicity adjustment approach will be described as per industry guidance for multiple comparisons across all the endpoints to eliminate Type 1 errors. Sensitivity analysis will be applied to handle missing data and sources of uncertainty. The protocol study team may revise the plan during the study to accommodate clinical trial protocol amendments and to make changes to adapt to unexpected issues in study execution and data that affect planned analyses. The protocol team will conduct all statistical analyses following the statistical principles for clinical trials as specified in International Council on Harmonization Topic E9. Any deviations from the planned analyses

will be described and justified in the final integrated clinical study report. The protocol study team will present overall and treatment specific data and summary tables.

All statistical tests will be two-sided. All summary tables for quantitative measures will display means, standard deviations, median and range, as well as number of missing data (if relevant). All summary tables for categorical variables will display counts, percentages, and number of missing data (if relevant).

10.3 Demographics and Baseline Characteristics

Demographics and baseline characteristics will include age, gender, race, comorbidities, baseline vital signs and laboratories. Descriptive statistics, including mean and standard deviation, median, intra-quartile ranges, minimum and maximum, and the number and percent of subjects in specified categories will be used to summarize the demographic and baseline variables for the two study arms. These will be compared between groups using independent two-sample test or Wilcoxon rank-sum test, as appropriate, for continuous variables and Fisher's Exact Test for categorical variables. All statistical analyses will be done using SAS statistical software.

10.4 Sample Size

This study will accrue approximately 66 patients in a 1:1 fashion to account for 10% attrition. This sample size was determined on the basis of an expected time to intubation event in the placebo group derived from historical data on critically ill patients with COVID-19 infection (SARS-CoV-2) of 3 days (72 hours) +/- 3 days (72 hours). An acceptable effect size in the intravenous citrulline group would be delay in time to an intubation event of at least 6.5 days (156 hours). Thus, a two-sided log-rank test with an overall sample size of 60 patients achieves 81% power at a 0.05 significance level to detect a hazard ratio of 0.46 when the placebo group time to intubation is 3 days. The study is expected to last 12 months, of which patient accrual will occur in the first 6-9 months. The accrual pattern across time is uniform.

In terms of mortality, in patients who progress to acute hypoxic respiratory failure requiring ICU care, the mortality is 50%. With a sample size of 60 patients, the study will have 80% power to detect a difference between the group proportions of -33%. The mortality in the intravenous citrulline group is assumed to be 50% under the null hypothesis and 17% under the alternative hypothesis. Again, the mortality rate for the placebo group is assumed to be 50%. The test statistic used is the two-sided z-test with pooled variance with a 0.05 significance level.

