2.0 STUDY SUMMARY

Title: Prospective, Randomized, Double-Blind, Placebo-Controlled Phase II Trial of Intravenous L-Citrulline to Delay and Potentially Prevent the Need for Invasive Mechanical Ventilation for Acute Hypoxemic Respiratory Failure in Patients with COVID-19 (SARS-CoV2) Illness.

Objective: To evaluate safety and efficacy of a bolus loading dose and continuous intravenous infusion of L-Citrulline compared to placebo in patients hospitalized with COVID-19 infection (SARS-CoV-2).

Hypothesis: Intravenous L-citrulline administration will safely restore the homeostasis of nitric oxide synthase by increasing both plasma citrulline and arginine levels. We also reason that restoration of citrulline/arginine balance through citrulline administration will safely re-establish homeostasis of NOS, lower oxidative stress, and reduce inflammation, thereby delaying and potentially preventing the need for invasive mechanical ventilation in patients hospitalized with COVID-19 infection (SARS-CoV-2).

Study Design:	
Prospective, randomized, placebo-controlled, double-blind design.
 
 1. Enrollment: approximately 6-9 months 2. Plasma citrulline and arginine levels at day 4 will represent the primary biochemical variable. 3. Vasomotor stability, as measured using a vasopressor dependency index (VDI), through study day 10, will represent the primary safety variable. 4. The length of time from the initiation of the treatment to an intubation event for invasive mechanical ventilation measured in hours will represent the primary clinical outcome. 5. Patients will be followed until hospital discharge for mortality, ICU and hospital lengths of stay, and a requirement for invasive mechanical ventilation and non-invasive mechanical ventilation with high flow nasal cannula or BiPAP as additional clinical endpoints. A further comparison will be performed at D28 and D60 based on telephone follow up for those discharged earlier. 6. Patients will exit the study early (prior to 10 days) if they recover and no longer require oxygen therapy.

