or NO production (3) Labeled citrulline leaves the plasma and is metabolized by a full turn of the urea cycle before reentering as arginine, (4) Oral administration of ^{15}N -arginine results in a nearly five-fold greater recovery of tracer in $^{15}\text{NO}_3$ than when an equimolar amount of tracer is given intravenously, documenting significant splanchnic production of NO. Administration of IV citrulline significantly bypasses the splanchnic circulation, thus limiting the splanchnic production of NO. (5) About 15% of the plasma arginine turnover is associated with urea formation; only 1.2% is associated with NO production. As arginase is upregulated in sepsis, the amount of arginine available as substrate for NOS is further reduced. Although this may decrease NO production somewhat (likely limited due to the low percentage of arginine converted to NO normally), it also alters homeostasis by uncoupling NOS and limiting the amount of NO available to scavenge free radicals. Citrulline is resistant to arginase and our data demonstrate that citrulline administration produces a more consistent plasma level of arginine than arginine administration itself.

3.4 COVID-19 (SARS-CoV2) and Acute Hypoxemic Respiratory Failure Requiring Invasive Mechanical Ventilation

Although reports in the US literature on COVID-19 (SARS-CoV2) and critical illness is limited, a recent case series published in the New England Journal of Medicine detailed the clinical course of 24 critically ill adults with acute hypoxemic respiratory failure and confirmed COVID-19 infection (SARS-CoV2) in Seattle, Washington at 3 hospitals in the University of Washington health care system (106). The mean age was 64 +/- 18 years with a range of 23-97 years and 63% were male. Patients had symptoms an average of 7 days before hospital admission. Of the 24 patients, 18 or 75% required invasive mechanical ventilation but after exclusion of 3 patients who had "do not intubate" directives the percentage was to 18/21 or 86% requiring invasive mechanical ventilation. The median duration of invasive mechanical ventilation was 10 days (IQR 7-12) and overall mortality was 50% in this critically ill population.

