6.2 Inclusion Criteria

Participant eligibility is determined based on the selection of criteria detailed below:

1. Age 18-65 years.
2. Clinical evidence of COVID-19 (SARS-CoV2) infection, defined as a positive COVID-19 laboratory test plus evidence of an acute hypoxic respiratory illness requiring oxygen.
3. Admitted and transferred to floor without intubation.

6.3 Exclusion Criteria:

Patients meeting any of the following criteria will not be eligible for participation in the study:

1. No consent/inability to obtain consent
2. Patient, surrogate, or physician not committed to full support
3. Malignant or other irreversible condition and estimated 28-day mortality $\geq 50\%$
4. Moribund patient not expected to survive 48 hours (as defined by primary medical team) from start of study infusion
5. End-stage Liver Disease as defined by Child-Pugh Score > 9
6. Currently enrolled in, or participated in another study of an investigational compound within the last 30 days
7. Pregnant female, or female who is breast feeding
8. Allergy to L-citrulline or arginine or any citrulline- or arginine-containing product
9. Patient not otherwise suitable for the study in the opinion of any of the investigators
10. Requirement for intubation and invasive mechanical ventilation before study enrollment

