## **SAMPLE SIZE**

This study will accrue approximately 66 patients in a 1:1 fashion to account for 10% attrition. This sample size was determined on the basis of an expected time to intubation event in the placebo group derived from historical data on critically ill patients with COVID-19 infection (SARS-CoV-2) of 3 days (72 hours) +/- 3 days (72 hours). An acceptable effect size in the intravenous citrulline group would be delay in time to an intubation event of at least 6.5 days (156 hours). Thus, a two-sided log-rank test with an overall sample size of 60 patients achieves 81% power at a 0.05 significance level to detect a hazard ratio of 0.46 when the placebo group time to intubation is 3 days. The study is expected to last 12 months, of which patient accrual will occur in the first 6-9 months. The accrual pattern across time is uniform.

In terms of mortality, in patients who progress to acute hypoxic respiratory failure requiring ICU care, the mortality is 50%. With a sample size of 60 patients, the study will have 80% power to detect a difference between the group proportions of -33%. The mortality in the intravenous citrulline group is assumed to be 50% under the null hypothesis and 17% under the alternative hypothesis. Again, the mortality rate for the placebo group is assumed to be 50%. The test statistic used is the two-sided z-test with pooled variance with a 0.05 significance level.

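### The 80% mortality power applies a death rate for patients who reach the ICU to all enrolled floor patients, so it does not describe the trial's population

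*Protocol*

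**What the plan says.** Protocol 10.4 and the SAP's Sample Size section carry the same mortality paragraph. It opens with a conditional rate: "In terms of mortality, in patients who progress to acute hypoxic respiratory failure requiring ICU care, the mortality is 50"%. It sets the treatment-arm assumption, "The mortality in the intravenous citrulline group is assumed to be 50% under the null hypothesis and 17% under the alternative hypothesis", and closes by giving the control arm the same 50%: "Again, the mortality rate for the placebo group is assumed to be 50"%. The claim built on these inputs is "With a sample size of 60 patients, the study will have 80% power to detect a difference between the group proportions of -33"%, and the method is "The test statistic used is the two-sided z-test with pooled variance with a 0.05 significance level".

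The enrolled population is defined in Protocol 6.2 and 6.3. Patients are 18 to 65 years old, test positive, have a hypoxic respiratory illness needing oxygen, and meet "Admitted and transferred to floor without intubation". Patients who needed intubation before enrolment are excluded, as are moribund patients. No criterion requires ICU care. Protocol 10.1 and the SAP's Analysis Populations section analyse all randomized patients.

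The only source described with 50% mortality is in the Protocol's introduction, in the section on COVID-19 and acute hypoxemic respiratory failure. It is a series of 24 critically ill adults, 18 of whom required invasive ventilation. Of their age the Protocol says: "The mean age was 64 +/- 18 years with a range of 23-97 years".

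The SAP tests hospital mortality with Fisher's exact test and adds a log-rank test and a hazard ratio for time to death. It specifies no interval for the difference in proportions.

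**The concern.** A death rate that applies after progression to ICU care is used as the death rate from randomization. The two agree only if enrolled placebo patients as a group die at the rate of ICU patients. Neither document says so, and neither gives the share expected to reach the ICU or a death rate for oxygen-requiring floor patients in this age range.

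All-cause hospital mortality is the first-listed secondary clinical endpoint and the only secondary endpoint with a power statement. If the true placebo rate is well below 50%, a non-significant mortality result could be read against an 80% figure that never applied to these patients. If placebo mortality is below 33%, the planned 33-point reduction cannot occur at all.

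**Working it through.** **1. Reproduce the plan's figure.** Inputs from Protocol 10.4: 30 per arm (60 patients, 1:1), p1 = 0.50, p2 = 0.17, two-sided alpha 0.05, pooled z-test.

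- Pooled rate: (0.50 + 0.17)/2 = 0.335.
- Standard error under the null: √(2 × 0.335 × 0.665 / 30) = 0.1219.
- Standard error under the alternative: √((0.50 × 0.50 + 0.17 × 0.83)/30) = 0.1142.
- Power = Φ((0.33 − 1.96 × 0.1219)/0.1142) = Φ(0.798) = 78.8%.

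This agrees with the stated 80% to within rounding, so the question is the 50% input and not the calculation. With Fisher's exact test, which the SAP plans, exact power on the same inputs is about 71% with 30 per arm and 76% with 33 per arm.

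**2. Express placebo mortality for the enrolled population.** Let f be the fraction of enrolled placebo patients who reach the ICU and m the mortality of those who do not. Then placebo mortality = 0.50f + m(1 − f). The documents give neither f nor m, so both are assumptions here. The table sets m = 0.

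**3. Choose an effect scale.** The plan states only an absolute difference of 33 points. Its two rates imply a relative risk of 0.17/0.50 = 0.34 and an odds ratio of (0.17/0.83)/(0.50/0.50) = 0.205. Each is held constant in turn, because the answer depends on the choice.

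**4. Power with 30 per arm, two-sided alpha 0.05.**

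| ICU fraction f | Placebo mortality | RR 0.34: treated rate | z-test | Fisher | OR 0.205: treated rate | z-test | Fisher |
|---|---|---|---|---|---|---|---|
| 100% | 50% | 17% | 79% | 71% | 17% | 79% | 71% |
| 75% | 37.5% | 12.8% | 60% | 50% | 10.9% | 68% | 58% |
| 60% | 30% | 10.2% | 48% | 36% | 8.1% | 58% | 46% |
| 50% | 25% | 8.5% | 40% | 27% | 6.4% | 51% | 36% |
| 40% | 20% | 6.8% | 32% | 17% | 4.9% | 42% | 25% |

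**5. Sensitivity to deaths outside the ICU.** With m = 5% and relative risk 0.34, z-test power at f = 75%, 60%, 50% and 40% is 62%, 51%, 44% and 37%. The loss is slightly smaller.

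**6. When is a 33-point reduction possible?** Only if placebo mortality is at least 33%. With m = 0 this means f of at least 0.33/0.50 = 66%. With m = 10%, f = 60% already gives 0.30 + 0.04 = 34%. Where the reduction is possible at a lower base rate, it is easier to detect: 37.5% versus 4.5% has z-test power of 90%, and 40% versus 7% has 87%.

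**7. Age of the source series.** If age is roughly normal with mean 64 and SD 18, about 44% to 48% of such a series lies above the trial's upper limit, depending on whether the limit is read as 65 or 66 and whether the curve is cut at the observed range.

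**The case against.** The strongest reply is that the statement does little work. Protocol 10.4 sets the sample size on time to intubation. Mortality is one of several secondary endpoints in a phase II trial, and the ICU condition is disclosed in the same paragraph. All of that is true, and it limits the weight of the point. It does not make 50% the right rate for an analysis of all randomized patients.

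Second, the replacement figures rest on choices that the documents do not make: the ICU fraction, deaths outside the ICU, the effect scale and the test. This also stands. No single corrected power can be given, only a labelled range.

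Third, some text anticipates ICU care. Protocol 5.1.1 speaks of delivering the infusion to the ICU, and 11.5 refers to a hospital unit or an ICU. ICU care may therefore be common, but eligibility does not require it and no fraction is stated.

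Several stronger readings are tempting, and the documents do not support them:

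- A reader might infer that most of the source series would have failed the floor-without-intubation criterion. The series reports that 18 of 24 required invasive ventilation. It does not report when, or their status on reaching the floor.
- A reader might take the early-exit rule, "Patients will exit the study early (prior to 10 days) if they recover and no longer require oxygen therapy", or the SAP's expectation that some patients will not need mechanical ventilation, as proof that patients avoid the ICU. Recovery of some patients is compatible with 50% mortality, and 6 of the 24 critically ill patients in the series were not ventilated.
- The exclusion for an estimated 28-day mortality of 50% or more applies to malignant or other irreversible conditions. It does not remove every patient at that level of risk.

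**Conclusion.** The point holds, at modest weight. A rate that the text limits to patients requiring ICU care is assigned to the whole placebo group of a floor-enrolled trial, so the 80% mortality power does not describe the population that will be analysed. The eligibility criteria and the all-randomized analysis set are enough to show this. The age of the source series adds some support, if that series is indeed the origin of the 50%; the power paragraph does not cite a source.

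For ICU fractions of 75% to 40%, no deaths outside the ICU and 30 per arm, power falls from about 60% to 32% (z-test) or 50% to 17% (Fisher) at a constant relative risk. At a constant odds ratio it falls from about 68% to 42% (z-test) or 58% to 25% (Fisher). The ICU fractions are illustrative and have no source in the documents.

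It would go too far to conclude that the 33-point effect is possible only if every patient reaches the ICU. At ICU fractions of 75% to 80% it remains possible. It is ruled out only when placebo mortality is below 33%, and the corresponding 66% ICU fraction assumes no deaths outside the ICU. Sample size, eligibility and the primary analysis are unaffected.

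**What to change.** In Protocol 10.4 and the SAP's Sample Size section:

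1. Replace the unconditional 50% with an assumed placebo mortality for the enrolled population, for example ICU fraction × 50% plus an assumed contribution from deaths outside the ICU. Label each component as an assumption and give its source if there is one.
2. Replace the single 80% with power over a range of placebo rates. Name the effect scale held constant, and compute power for the Fisher's exact test that the SAP plans.
3. State that a 33-point reduction is impossible if placebo mortality is below 33%, and make no claim of adequate power for mortality.
4. In the SAP's mortality analysis, add the difference in proportions between arms with a 95% confidence interval.

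The cost is a rewording in two sections and one added output in the mortality analysis. The stated mortality power becomes less favourable. No extra patients or data are needed.
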